### 9.4.3 Secondary analyses

Both the effect of cell administration and the effect of the timing of cell administration will be evaluated for each of the secondary endpoints. Using general linear model procedure, the effect of cell administration on LV mass, end diastolic volume, end systolic volume, and infarct size will be assessed. The analysis variable will be the change in LVEF (either global or regional) from the immediate pre-infusion level to six months. Both unadjusted and adjusted treatment effects will be computed; adjustments will be for baseline covariates whose association with the dependent variable is generally accepted. Logistic regression will be used to assess the effect of cell administration on the combined endpoint of death, reinfarction, repeat revascularization, and hospitalization for HF.

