#### 3.2.5 Stratification

Patients will be stratified by Clinical Center.

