### **8.0 ENDPOINT EVALUATION AND CLASSIFICATION**

A cardiac MR 1.5 T scanning unit (Avanto, Cardiac MR Scanner, Siemens Medical Systems or equivalent) will be used for cardiac MR images. The exact cMRI Scanner will vary at each institution, however, the exact imaging protocols will be established by the MRI Core Lab. cMRI was chosen by the Network to evaluate the primary and secondary endpoints because it is independent of the geometric assumptions required for calculations of ejection fraction compared to echocardiography or left-ventriculography. Furthermore, the inter-study reproducibility for cMRI is significantly better than echocardiography for measurements such as LVEF, LVEDV, LVESV and cardiac mass (36, 37). However, the patient's measurements of global LVEF from entry into the study until

completion will be assessed by echocardiography in place of cMRI when MRI is contraindicated.

A series of scout images will be required with a pulse sequence that collects an image in a fraction of the RR interval. Scout imaging will start with a transverse view at the mid-ventricular level. Using the first scout as a localizer, the technologist will acquire the next scout image for the image plane that intersects with the long axis of the LV. A horizontal long axis cine series (four chamber view) will be acquired first followed by the long axis cine (twp chamber view). The image planes for the short axis studies will start at the base of the heart, at least two cm above the mitral-tricuspid valve plane to achieve maximal LV coverage. Using Tru-FISP (balanced- FFE) cineangiography, the slices will be consecutively positioned every 7 mm from the base to apex with a 3 mm interslice gap. The acquisition window for retrospectively-triggered cine sequence will be obtained. End-expiratory breath-hold with sampling throughout the entire cardiac cycle will be employed because of better reproducibility of each slice position for more accurate left ventricular volume analysis. A minimum of 20 cardiac phases will be used to cover the RR interval. All patients will undergo baseline cMRI measurements at Day 3 given that resolution of myocardial stunning and improvement in global and regional LV function often continues to occur between Day 3 and Day 7 which would negatively bias the Day 7 group when LV function is reanalyzed at six months.

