### 9.0 STATISTICAL PROCEDURES

#### 9.1 Randomization

Once informed consent has been obtained, eligible patients will be entered into the study randomly assigned to one of the selected treatment strategies in an interactive Web-based randomization session where exclusion and eligibility criteria will be assessed. Patients will be randomized to the time of administration (Day 3 or Day 7) using a variable block size of 4 or 6. Patients will be randomized to therapy type (active or control therapy), using variable block sizes of 3 or 6, randomly selected. Patients will be stratified by clinical center. When a patient is randomized, the clinic will be given an identification (ID) number and acrostic, specific information on the assigned treatment regimen, and a list of procedures to be completed at the baseline visit. A participantspecific schedule of visits and procedures will be displayed for printing locally. The DCC will monitor patient recruitment by providing reports to the Core Laboratories and Project Office (PO) as appropriate during the recruitment phase. Updated reports will be maintained on an Internet site accessible to all units of the study. The recruitment reports will provide data on recruitment of women and minorities (African-Americans, Hispanics, and Asians). Goals for recruitment will be set and will be reviewed by the DCC and PO.

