### 9.4.2 Co-primary endpoint evaluations

Each primary endpoint, global LVEF(%) and regional LV function is a continuous variable. General linear mixed modeling techniques will be utilized to assess the effect of treatment on the primary endpoint of the study. For patients recruited to the Day 3 arm of the study, the six month MRI will be compared to the Day 3 MRI. For patients recruited to the Day 7 treatment group, the six month MRI will be compared to the Day 7 MRI

The analysis variable will be the change in LVEF (either global or regional) from the immediate pre-infusion level to six months. Both unadjusted and adjusted treatment effects will be computed; adjustments will be for clinical site as well as for baseline covariates whose association with the dependent variable is generally accepted. In keeping with standard methodology for clinical trials, the primary analysis will compare the randomized study groups.

Despite the efforts of CCTRN Investigators to ensure that patients return to their center for follow-up evaluation, we anticipate that a small number of subjects will be unable to return for their follow-up endpoint assessment. Last observation carried forward analyses will be carried out as supportive evaluations.

Anticipating this difficulty, the sample size for this study has been increased by a small percent, allowing the Investigators to capture complete data on a number of patients as close to the pre-specified sample size as possible. However, for those patients who are missing the final six month endpoint data, we will carry out a Last Observation Carried Forward (LOCF) analysis. For a patient who is missing the follow up information, the value of the follow-up measure will be assumed to be equal to their base-line value. Thus the difference in the endpoint measure over the six month follow-up will be zero. While a large number of missing data points, corrected in this matter can produce a bias toward the null, this standard LOCF procedure will be adequate for the small number of patients with missing data.

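### Section 9.4.3 leaves clinical site, the only stratification factor, out of the adjusted models for the four continuous secondary endpoints, although 9.4.2 includes it for the co-primary endpoints

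*Protocol*

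**What the plan says.** Clinical center is the only stratification factor that the protocol names. Section 3.2.5 says "Patients will be stratified by Clinical Center", and Section 9.1 repeats it when describing the blocked assignment to timing (blocks of 4 or 6) and to therapy (blocks of 3 or 6).

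The two analysis sections then differ:

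- **9.4.2, co-primary endpoints:** both unadjusted and adjusted effects are planned, and "adjustments will be for clinical site as well as for baseline covariates whose association with the dependent variable is generally accepted".
- **9.4.3, secondary endpoints:** the model is given as "Using general linear model procedure, the effect of cell administration on LV mass, end diastolic volume, end systolic volume, and infarct size will be assessed", and the adjustment sentence reads "Both unadjusted and adjusted treatment effects will be computed; adjustments will be for baseline covariates whose association with the dependent variable is generally accepted". Site is not named.

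Section 9.4.1 says in general terms that continuous outcomes will be analysed with a general linear mixed model. It names no random effect and does not mention site.

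**The concern.** When treatment is blocked within centers, the arms are balanced across centers by design, so differences between centers largely cancel from the treatment contrast. A model without center does not know this. It counts between-center variance as residual error and reports a standard error larger than the true variability of the estimate. Confidence intervals are then wider than they need be, and a nominal 5% test rejects less than 5% of the time under the null.

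The four endpoints come from the same patients, centers and cardiac MRI examinations as the co-primary endpoints. Nothing in the protocol explains why the stratification factor belongs in one set of adjusted models and not in the other. An analyst following 9.4.3 literally would leave it out. One who preferred consistency with 9.4.2 would put it in. That choice should not be open once results are visible.

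**Working it through.** **The plan's own figure.** The protocol gives no standard deviation, standard error or power for any secondary endpoint. The nearest figure is the 94.9% power for global LVEF in 3.2.6.3.1: 80 active and 40 control patients, 5% loss (76 and 38), difference 5, SD 7, two-sided 0.0495.

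- SE = 7 × √(1/76 + 1/38) = 7 × 0.1987 = 1.391
- 5 / 1.391 = 3.595; 3.595 − 1.964 = 1.631; power = 0.9485

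The stated figure reproduces, but it contains no site term and concerns no secondary endpoint. It supplies a scale only.

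**Effect of leaving site out.** Let ρ be the share of outcome variance that lies between centers. The documents give no value, so a range is assumed. With very many centers, the ratio of the model SE without site to the SE with site is 1/√(1 − ρ). With only five, part of the between-center variance goes into the overall mean, and the ratio is

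ratio = √[1 + ρ(1 − Σp²)/(1 − ρ)],

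where p is each center's share of patients. The annual projections in Table 13 (11, 25, 11, 13 and 11, total 71) give Σp² = (3 × 121 + 625 + 169)/5041 = 0.2295, so 1 − Σp² = 0.7705.

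- ρ = 0.05: √(1 + 0.05 × 0.7705/0.95) = √1.0406 = 1.020
- ρ = 0.10: √(1 + 0.10 × 0.7705/0.90) = √1.0856 = 1.042

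**Simulation.** Five centers in the Table 13 proportions were simulated, with about 114 evaluable patients (115 after rounding within centers), 2:1 blocks of 3 or 6, SD 7 and 4,000 trials per setting. A separate run used five equal centers of 24 with blocks of 3 and 2,500 trials per setting.

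| Assumed ρ | 1/√(1 − ρ) | Simulated mean SE, without / with site | Ratio | Ratio, five equal centers |
|---|---|---|---|---|
| 0 | 1.000 | 1.381 / 1.382 | 1.000 | not run |
| 0.02 | 1.010 | 1.376 / 1.366 | 1.008 | not run |
| 0.05 | 1.026 | 1.374 / 1.347 | 1.019 | 1.344/1.315 = 1.022 |
| 0.10 | 1.054 | 1.367 / 1.311 | 1.043 | 1.339/1.283 = 1.044 |

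**Test level.** With ratios 1.020 and 1.042, the effective critical values are 1.96 × 1.020 = 2.00 and 1.96 × 1.042 = 2.04. The two-sided levels are therefore about 0.046 and 0.041. The 4,000-trial simulation gave 0.043 and 0.042 without site, and 0.047 and 0.051 with it. Its Monte Carlo error is about √(0.05 × 0.95/4000) = 0.003, so the rejection rates are less precise than the SE ratios.

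**What does not change.** At ρ = 0.10 the actual spread of the estimate across simulated trials was 1.322 without site and 1.321 with it. The blocking already protects the point estimate. Only the reported standard error is affected.

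**Cost of the site term if center does not matter.** Residual degrees of freedom fall from 112 to 108. At ρ = 0 the interval without site is 0.9996 times the width of the interval with site, so the loss is negligible.

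**The case against.** The strongest reply is that this is a wording difference with an unknown and possibly nil consequence. Much of it stands, and it rules out several stronger readings.

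- *That the standard errors are in fact too wide.* A reader might infer this from the omission alone. It is true only if center explains variance in the changes, and the documents do not say that it does.
- *That the protocol itself predicts center differences.* Section 8.0 does say "The exact cMRI Scanner will vary at each institution", but the same sentence has the MRI core laboratory set the imaging protocols. A stable scanner offset would also largely cancel from a change score. Section 4.2 plans to assess differences in post-MI care between centers rather than predicting them, and it requires all investigators to follow standard management. Cell processing uses one closed system, and since only active patients receive cells, laboratory differences would show mainly as a site-by-treatment interaction, which a site main effect does not capture. A center effect is plausible but not established.
- *That patients are wasted.* A variance share of 5% to 15% might be read as 6 to 18 of 120 patients lost. The standard errors in the equal-centers run imply 1 − (1.315/1.344)² = 4.3% to 1 − (1.246/1.331)² = 12.4%, or about 5 to 15. Even that describes the reported precision, because the estimate itself loses essentially nothing.
- *That 9.4.3 forbids a site term.* It does not. The mixed-model statement in 9.4.1 leaves room for one, but none is stated there, so it does not settle the matter.

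It can also be said that covariate lists belong in the statistical analysis plan, which is not at hand. That would answer a silent protocol. Here the protocol states an adjustment set, and it differs from the one in the section just before it.

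**Conclusion.** The point holds as an unexplained inconsistency in the adjusted analyses. The only stratification factor is in the co-primary adjustment set and missing from the one stated for LV mass, the two volumes and infarct size. The unadjusted analyses omit site in both sections, so they are not part of the contrast.

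The consequence is conditional and small. The model standard error is about 2% too large at an assumed between-center share of 5%, about 4% at 10%, and unaffected at 0%. The error is conservative, so it cannot create a false positive. These figures assume five centers, 2:1 blocking within center and a common center effect in both arms. The ratios do not depend on the SD of 7, which belongs to global LVEF. The change is worth making because it is nearly free and removes an open choice, not because the secondary results would otherwise be misleading.

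**What to change.** In 9.4.3, extend the adjustment sentence so that clinical site is included with the baseline covariates for LV mass, LVEDV, LVESV and infarct size, as 9.4.2 already does ("adjustments will be for clinical site as well as for baseline covariates"). If leaving site out was intended, state the reason instead. The unadjusted estimates can be reported alongside, as in 9.4.2. That section ranks neither estimate above the other, so consistency does not require making the site-adjusted one the main result.

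The cost is a few words in the protocol, the same term in the analysis plan, and four degrees of freedom. The same edit can correct a separate slip in that paragraph, which names the change in LVEF as the analysis variable for endpoints that are not LVEF. That suggests the text was carried over from 9.4.2.

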## Secondary endpoints

- 1. Combined endpoint (first of) death, reinfarction, repeat revascularization, hospitalization for HF
- 2. LV mass
- 3. End diastolic volume
- 4. End systolic volume
- 5. Infarct size

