## 1.2 Secondary Objectives

The secondary objective of this study is to determine the effect of BMMNC when compared to placebo on the change from baseline to six months on each of LV mass, LV systolic and end-diastolic dimensions, and infarct size over six months. The influence of time of administration on BMMNC effect for each of these measures of LV function will be assessed. In addition, adverse events (AE) including hospitalization for HF will be assessed two years post randomization.

This protocol is consistent with the scope of the CCTRN to accelerate research in the use of cell-based therapies for the management of cardiovascular diseases.

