To address the above limitations we have proposed a randomized, blinded, placebocontrolled, clinical study of autologous BMMNC administration to 120 patients following AMI. To further evaluate the potential efficacy of this therapy, enrollment will be limited to patients with moderate to large infarctions with no prior history of CABG and whose ejection fraction following revascularization is <45%. The primary end-point of the study will be change in regional and global LV function (LVEF) at six months compared to baseline as measured by cMRI. Patients will be followed for two years to evaluate the effect of this therapy on clinical end-points such as death, repeat revascularization, MI and hospitalization for HF. Patients will be randomized in a 2:1 ratio of stem cell treatment to placebo. Because the important question of timing of cell delivery post-MI has never been addressed in any clinical study, the patients will be randomized to cell therapy at two physiologically distinct time points. Additionally, this will be the first clinical trial to administer the same dose of cells to all patients. To accomplish this we will administer 150 x 10^6 TNCs (70-80% BMMNC) to all patients at the pre-specified times of three versus seven days post-MI. It is the intention of this Phase II study to establish time points for delivery of BMMNC following MI that potentially can be used as the basis for a larger clinical Phase III study using either BMMNC or a more enriched cell type such as CD34+. A secondary goal of this trial will involve the establishment of a biorepository to examine how cell phenotype (cytokine and nitric oxide production, etc.) may affect therapeutic efficacy.

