## 3.2.6.3.1 Effect of BMMNC infusion on global ejection fraction

Assume 80 active group patients and 40 control patients. We are assuming an absolute change  $\delta = 5$  and common group standard deviation of the difference of LVEF over time as  $\sigma(\Delta)_{LVEF} = 7$ , Type I error (two-tailed) = 0.0495. We anticipate that 5% of patients will be lost to follow-up. The standard deviation of the change in ejection fraction from baseline to six months is 7.0. These assumptions are based on the findings from the Wollert (24), Lunde (17), Schächinger (20), and Janssens (16) articles. Under these assumptions, the power is 94.9. A table displaying the sensitivity of the power computation to assumptions concerning treatment effect and standard deviation of the difference is provided (Table 7).

		Treatment Effect (δ)				
		4	5	6	7	8
Std Dev	5	0.981	0.999	1.000	1.000	1.000
of Diff	6	0.919	0.987	0.999	1.000	1.000
(σ)	7	0.820	0.949	0.991	0.999	1.000
	8	0.711	0.882	0.965	0.993	0.999

Table 7. Power for the effect of dose on lobal Ejection Fraction
Type I error = 0.05; N=120; 2:1 active:placebo ratio followup losses = 5%

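### Section 9.4.3 names change in LVEF as the analysis variable for LV mass, volumes and infarct size; secondarily, its logistic regression for the two-year composite cannot handle patients who leave event-free

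*Protocol*

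**What the plan says.** **Imaging endpoints.** Section 9.4.3 prescribes a general linear model by which "the effect of cell administration on LV mass, end diastolic volume, end systolic volume, and infarct size will be assessed". The next sentence defines the dependent variable: "The analysis variable will be the change in LVEF (either global or regional) from the immediate pre-infusion level to six months". The same sentence stands in section 9.4.2, where the endpoints are global and regional LVEF and it fits. Section 1.2 describes the secondary comparison differently, as "the change from baseline to six months on each of LV mass, LV systolic and end-diastolic dimensions, and infarct size over six months".

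**Composite.** The Executive Summary defines it as "Combined endpoint (first of) death, reinfarction, repeat revascularization, hospitalization for HF". Section 2.1.4 adds: "Patients will be followed for two years to evaluate the effect of this therapy on clinical end-points". Section 1.2 likewise places the assessment of adverse events, including heart failure hospitalisation, at two years after randomisation. Section 9.4.3 then says: "Logistic regression will be used to assess the effect of cell administration on the combined endpoint".

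Section 9.4.3 gives no horizon for the composite, and no time-to-event method appears anywhere in the protocol. The only missing-data rule, in section 9.4.2, sets a missing six-month measurement equal to its baseline value. The only loss figure, "We anticipate that 5% of patients will be lost to follow-up" (section 3.2.6.3.1, with the same 5% in the other sample size sections), belongs to the six-month calculations.

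**The concern.** The two parts differ in weight.

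The first is a stated analysis rule that is wrong. The Executive Summary lists five secondary endpoints, and four of them (LV mass, the two volumes, infarct size) fall under the LVEF sentence. Two of the three secondary hypotheses, smaller end-diastolic and smaller end-systolic volumes, depend on those four. A programmer who follows section 9.4.3 would analyse LVEF a second time.

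The second is a mismatch of method and endpoint. A binary regression needs every patient's status at one common time. A patient who leaves event-free at, say, month 14 of 24 must be excluded or counted as event-free. The protocol chooses neither, and the two choices push the estimate in opposite directions when loss differs between arms. If the choice is still open once outcomes are known, it can be influenced by them.

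**Working it through.** **1. Dependent variable (no arithmetic applies).**

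| Place | Endpoints concerned | Dependent variable |
|---|---|---|
| Section 9.4.2 | Global and regional LVEF | Change in LVEF, pre-infusion to six months |
| Section 1.2 | LV mass, LV dimensions, infarct size | Change in each measure, baseline to six months |
| Section 9.4.3 | LV mass, two volumes, infarct size | Change in LVEF, pre-infusion to six months |

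The third row takes its endpoints from the second and its variable from the first. Sections 1.2 and 9.4.3 cannot both be right, and only section 1.2 answers the secondary question.

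**2. Composite.** The protocol gives no event rate, effect size or power for any secondary endpoint, so there is no figure to reproduce. What follows is an illustration.

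From the documents: 80 active and 40 placebo patients, and two years of follow-up. Assumed: two-year event risk p of 10% to 30%, equal in both arms (no true effect); two-year loss l of 5% to 20%; exponential, non-informative event and dropout times.

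With h = −ln(1 − p), g = −ln(1 − l) and T = 1 − (1 − p)(1 − l):

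- share with an observed event: E = T·h/(h + g)
- share lost event-free: L = T·g/(h + g)
- odds if the lost are coded event-free: E/(1 − E)
- odds if the lost are excluded: E/(1 − L − E)

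Worked case, p = 20% (h = 0.223), loss 15% active and 5% placebo:

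- Active: g = 0.163, T = 1 − 0.80 × 0.85 = 0.32, E = 0.185, L = 0.135.
- Placebo: g = 0.051, T = 1 − 0.80 × 0.95 = 0.24, E = 0.195, L = 0.045.
- Coded event-free: odds ratio (0.185/0.815)/(0.195/0.805) = 0.94.
- Excluded: risks 0.185/0.865 = 0.214 and 0.195/0.955 = 0.204, odds ratio 1.06.

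Over p = 10% to 30%, true odds ratio 1:

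| Loss, active vs placebo | Lost coded event-free | Lost excluded |
|---|---|---|
| 5% vs 5%, 10% vs 10% | 1.00 | 1.00 |
| 5% vs 15% | 1.06–1.07 | 0.94 |
| 15% vs 5% | 0.93–0.94 | 1.06 |
| 5% vs 20% | 1.10–1.12 | 0.91 |

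A censored time-to-event analysis has hazard ratio 1.00 in every row, given non-informative dropout.

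**3. Patients affected.** With 5% to 15% lost overall, exclusion removes 120 × 0.05 = 6 to 120 × 0.15 = 18 patients. Coding them event-free misclassifies only those with a later event. At a 20% two-year risk and departure at mid-follow-up, about 10% risk remains, so 6 × 0.10 = 0.6 to 18 × 0.10 = 1.8 patients.

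**4. Bias against noise.** At 20% risk, 16 of 80 and 8 of 40 patients have events. SE(log odds ratio) = √(1/16 + 1/64 + 1/8 + 1/32) = 0.48. The bias is |ln 0.937| = 0.065, and 0.065/0.48 = 0.13 standard errors.

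**The case against.** On the imaging endpoints, the other side can say that this is a copying slip whose meaning nobody would miss: the preceding sentence of section 9.4.3 lists the right endpoints and section 1.2 gives the right variable. That is fair as to intent. A reader might infer that the four endpoints would go unanalysed, and the documents do not support that; they show a wrong definition, with the right one elsewhere. It still has to be corrected, because it is the operative statement in the statistical section.

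On the composite, the case is stronger. The protocol treats clinical outcomes as binary throughout: the secondary hypothesis speaks of incidence, section 5.4.7 assigns logistic regression to dichotomous outcomes, and section 9.5 calls the clinical endpoints dichotomous. Defining a composite by its first event does not oblige a time-to-event analysis. At a fixed horizon with complete follow-up, logistic regression is valid. With equal loss there is no bias under the null, and in a blinded trial a large difference in loss is not to be presumed. Horizon and handling of lost patients are also details that an analysis plan, not shown here, may settle. All of this stands, and it limits this part to an improvement.

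Two further inferences are tempting. One is that logistic regression would misclassify 6 to 18 patients; that count applies to exclusion, and the expected number misclassified is about 0.6 to 1.8. The other is that a Cox model would recover useful power; the calculations show no such gain, and the argument here rests on follow-up, not precision.

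**Conclusion.** The first part holds without assumptions: section 9.4.3 gives the wrong dependent variable for four of the five secondary endpoints and contradicts section 1.2.

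The second part holds as a moderate point. The named method cannot use partial follow-up on an endpoint followed for two years, and the protocol has no rule for patients who leave event-free. Under the null the expected bias in the odds ratio is nil with equal loss, about 6–7% with a 10-point difference in loss between arms, and about 9–12% with a 15-point difference. The event risks, loss rates and non-informative dropout behind these figures are assumptions. At the 10-point difference the bias is small beside the sampling error of a 120-patient trial. The documents do not support calling logistic regression invalid here.

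**What to change.** **Correction (wrong as written).** In section 9.4.3, replace the LVEF sentence with:

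> The analysis variable is the change from baseline, as defined for the co-primary endpoints, to six months in the endpoint concerned (LV mass, LVEDV, LVESV, infarct size).

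This deliberately leaves the baseline scan open. Section 8.0 takes Day 3 as baseline for all patients, while section 9.4.2 compares the Day 7 arm with its Day 7 scan. That conflict must be reconciled separately and need not delay this correction. The cost is one sentence.

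**Improvement.** Analyse the composite as time from therapy randomisation to first event through 24 months, censored at last contact, with Kaplan–Meier curves, a log-rank test and a Cox model. Keep logistic regression as supportive, with its horizon and its rule for patients lost before that horizon stated in advance. The cost is a little more analysis work and the need for event dates. Section 7.3 requires events to be recorded on the case report forms but does not expressly list dates, so this should be confirmed. Both changes should be made before unblinding.
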